1. Develop the scoring algorithm, including minimum number of items requiring response to score. DHI scores are continuous and based on summed means of scale items with higher values indicating better health.
2. Evaluate scale score distributions; evaluate for floor and ceiling effects $\geq 10\%$ response at the tails.

Analysis of Key Psychometric Properties:

1. Factor Structure: principle components (PCA) and principle factor analysis (PFA) methods that included orthogonal (varimax) and oblique rotation (promax).^{39,40} Eigenvalue statistics are used to evaluate the strength of these relationships; a high eigenvalue indicates that an underlying subscale exists and low values indicate that the underlying subscale might not exist. If a subscale's eigenvalue meets the threshold for retention, the next step in the analysis is to evaluate how items relate to a particular factor using factor loading scores. We used standard criteria (eigenvalues > 1) and items within factors (factor loading scores > 0.40)^{39,40} in our iterative scale development process.

2. Internal Validity: Internal dimensional validity of scales was evaluated using factor analysis (FA). Initially, exploratory FA of item grouping within the 3 hypothesized domains (physical, mental, and social health) was conducted to identify factors within each domain, followed by a confirmatory FA of all items within those factors of all domains. The final factor loadings are a result of the confirmatory analysis. Internal consistency was evaluated with Cronbach's alpha. Items with factor loadings < 0.40 were dropped for low convergent validity; items with loadings > 0.9 were reviewed for redundancy and dropped as appropriate.

3. Test-retest Reliability: Reliability analyses included individuals who completed the retest survey. Test-retest reliability of each subscale score was assessed through the interclass correlation coefficient (ICC). An item was used to screen out individuals who experienced major changes in status between the test and the retest. Test-retest reliability was evaluated with paired t-tests and chi square tests at the item level and 2-way mixed-effects intraclass correlation coefficient (ICC) models at the scale level, with a 95% confidence interval of the estimate using the following guideline: poor (< 0.5), moderate ($0.5-0.75$), good ($0.75-0.9$), and excellent (> 0.90).

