4. External Criterion / Construct Validity: In the criterion validity evaluation, Pearson correlations served as the primary evaluation technique to evaluate how scores on our new measure correlated with scores on other external measures of components of health status (the PEDSQL, the SDQ, the CSHQ). Published scoring algorithms were used whenever available. General MOS items were scored using a simple mean.

We are seeking to establish validity to draw a valid inference about a distribution and establish some basic inferential validity. External validity will be operationalized using a multitrait-multimethod matrix (MTMM) approach, with the "gold standard" being establishment of forms of both convergent and divergent (discriminatory) validity.⁶² For validation of the DHI, each domain is considered a trait. Method refers to a measurement procedure, which includes consideration of both data source as well as data collection method. The referent method is a caregiver-administered survey. The data source is DHI respondent proxy-report for an individual with DS. The data collection methods include survey instruments and medical record review of clinically-significant metrics. Generally, correlation

coefficients between DHI domains and data external to the DHI will be used as evaluative criteria, with the specific correlation statistic being determined by the test value variable type. Utilization of the MTMM allows evaluation of correlation within and between methods and sources as well as within and between dimensions or traits.

Subgroup Analyses

We anticipated analysis by mode (PAPI vs CASI) but found that nearly all individuals elected to complete CASI.

All analyses were conducted using SAS® (v. 9.4).

All analyses were conducted using SAS, version 9.4 (SAS Institute, Cary, NC) and R, version 2.1.9 (R Core Team, Vienna, Austria), with R package psych. The protocol was registered ([ClinicalTrials.gov](https://clinicaltrials.gov/ct2/show/study/NCT04631237); NCT04631237).

This study was approved by the MGB Institutional Review Board. De-identified supporting data are available upon request from the authors.

Changes to Statistical Analysis Plan

Section	Original	Final
Power Calculation	Planned 70 items in final pool	113 core items in final pool
Determining Complete surveys	-	Added information regarding determination of “Complete” survey
Item-level evaluation	-	Added details regarding missingness and handling missing data

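### The final SAP states no item-level rule that would detect an item measuring a domain other than the one it was assigned to

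*SAP*

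**What the plan says.** Under Analysis of Key Psychometric Properties, item 2 (Internal Validity), the final SAP states that "exploratory FA of item grouping within the 3 hypothesized domains (physical, mental, and social health) was conducted to identify factors within each domain". A second step then takes in every domain; the exploratory work was "followed by a confirmatory FA of all items within those factors of all domains". On which loadings count, the SAP adds: "The final factor loadings are a result of the confirmatory analysis". Two item rules are given. The lower one reads "Items with factor loadings < 0.40 were dropped for low convergent validity"; for the upper one, the SAP says that "items with loadings > 0.9 were reviewed for redundancy and dropped as appropriate".

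Item 1 (Factor Structure) names principal components and principal factor methods with varimax and promax rotation, eigenvalues above 1 and loadings above 0.40. It does not say whether items were pooled or taken domain by domain.

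On scoring, the Survey-level Evaluation section says: "DHI scores are continuous and based on summed means of scale items with higher values indicating better health". Item 4 (External Criterion / Construct Validity) sets up a multitrait-multimethod matrix (MTMM) that seeks convergent and divergent validity: "For validation of the DHI, each domain is considered a trait".

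**The concern.** The exploratory step sees only the items already filed under a domain, so it cannot show that an item fits another domain better. The CFA is then built on the factors from that step. Both item rules concern the size of a loading; neither compares one domain with another.

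Health domains are likely to be correlated. An item filed under physical health that really measures mental health will then still load on the physical factor, and may clear 0.40. Several such items can form a clean factor of their own inside the wrong domain. Because scores are built from item means, these items enter the wrong score directly. They also pull the domain scores together, which weakens the divergent validity that the MTMM is meant to show. The MTMM can reveal that two domain scores are close, but not which item is responsible.

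**Working it through.** **Inputs from the SAP.** Analysed sample 542 (Determining Complete Surveys); 113 core items; cut-offs 0.40 and 0.9; eigenvalue above 1. The plan gives no figure on this point to reproduce.

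**Assumptions (not in the documents).** Correctly placed items load 0.6. A misfiled item loads λ = 0.6–0.8 on the other domain and zero on its own. Domain correlation φ is 0.3–0.8.

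**Step 1: one misfiled item, one factor per domain.** Its apparent loading on the assigned factor is λ × φ. It reaches 0.40 when φ ≥ 0.40/λ: 0.40/0.8 = 0.50, 0.40/0.7 = 0.57, 0.40/0.6 = 0.67.

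**Step 2: the same item in an all-domain CFA.** Population calculation with three domains of 10 items, λ = 0.7, and cross-loadings fixed at zero (the SAP does not say whether they are). Expected chi-square excess is 541 × F, where F is the minimised fit function, and RMSEA = √(F/df) with df = 402. For φ = 0.3: F = 263.9/541 = 0.488 and RMSEA = √(0.488/402) = 0.035.

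| φ | EFA loading | CFA loading | RMSEA | Chi-square excess | Largest residual with a mental item | Fitted physical–mental correlation |
|---|---|---|---|---|---|---|
| 0.3 | 0.21 | 0.25 | 0.035 | 264 | 0.37 | 0.33 |
| 0.5 | 0.35 | 0.41 | 0.031 | 213 | 0.28 | 0.55 |
| 0.6 | 0.42 | 0.49 | 0.028 | 175 | 0.23 | 0.66 |
| 0.7 | 0.49 | 0.57 | 0.024 | 130 | 0.16 | 0.76 |
| 0.8 | 0.56 | 0.63 | 0.019 | 78 | 0.10 | 0.85 |

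The item passes 0.40 in the CFA from φ = 0.5. RMSEA is low throughout. The residuals carry the warning, and the SAP does not say that they are inspected.

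**Step 3: sampling at n = 542, one misfiled item.** Share of samples in which it is kept:
- One factor per domain: λ = 0.8 gives 47–55% at φ = 0.5 and 97–100% at 0.6, across repeated runs; λ = 0.7 gives 8–11%, 66–70% and 98–100% at 0.5, 0.6 and 0.7; λ = 0.6 gives 0% at 0.5 and 16% at 0.6.
- Three factors per domain (six items each, factors correlated 0.5, varimax): 0–1% at λ = 0.8, φ = 0.5; 24–26% at 0.8, 0.6; 4% at 0.7, 0.6. Promax gave 0% in these three cases.
- Over λ = 0.6–0.8 and φ = 0.3–0.7 the ranges are 0–100% (one factor) and 0–91% (three varimax factors). At φ = 0.3 both are near 0%.

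**Step 4: three items misfiled together.** In the Step 2 set-up with λ = 0.7, they form their own factor inside the physical domain at φ = 0.3–0.7, with EFA loadings 0.67–0.69 and CFA loadings 0.70. RMSEA is 0, and that factor correlates 1.00 with the mental factor. At φ = 0.8 they stay on the single physical factor (EFA 0.62, CFA 0.68), and the fitted physical–mental correlation is 0.94 against a true 0.80. In sampling with three own factors and a fourth extracted, all three items are kept in 79–100% of samples, except 10% at λ = 0.6, φ = 0.7. Where the eigenvalue rule retains only three factors, as it usually does at φ = 0.7, the share is lower for λ = 0.6 and 0.7.

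**Step 5: would an item-by-scale table find them?** For ten-item scales, the standard deviation of the scale mean is √((1 + 9 × 0.36)/10) = 0.651. With λ = 0.7 and φ = 0.6, the misfiled item correlates 0.7 × 0.6 × 0.6/0.651 = 0.387 with its assigned scale and 0.7 × 0.6/0.651 = 0.645 with its true one. In simulation the comparison flagged single misfiled items in 100% of samples and all three grouped items in 81–100%, with no false flags for correctly placed items.

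**The case against.** A reader might infer that nothing in the plan looks across domains. The documents do not support that: the CFA takes in all domains' items and supplies the final loadings, and the MTMM compares domains at score level.

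Nor does the SAP say that cross-loadings are fixed at zero or that items could not move. The Original Proposed Statistical Analysis Plan speaks of a CFA that might or might not reveal the hypothesised factors, which hints at a joint analysis with free loadings. The Factor Structure paragraph may also describe a pooled, rotated analysis. A pooled analysis would expose the item: in the Step 2 set-up it loads about 0.60–0.69 on its true factor and at most about 0.26 on the others.

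The high retention rates for a single item also depend on one factor per domain and strong domain correlation. The SAP looks for several factors within each domain, and there the 0.40 rule usually removes a lone misfiled item unless φ is about 0.7 and λ is high.

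All of this stands, and it limits the point to what is stated. It does not remove it. Even if loadings were free, no rule says what happens to an item that loads as highly elsewhere. Items misfiled as a group can pass 0.40 even at low domain correlation, and global fit need not reveal them.

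**Conclusion.** The concern holds as a gap in the stated item rules with a concrete consequence: the all-domain CFA is not shown to detect an item that measures another domain. Such an item can survive when domains are strongly correlated, or when several items are misfiled together.

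The size is conditional. Loadings, domain correlations and factor structure are all assumed here. The risk from one item runs from nil to near certainty across the range tried. For three items together it is high in most scenarios, given that their factor is retained. One misfiled item in ten raises the fitted domain correlation by only 0.03–0.06 (Step 2); three raise it by 0.14 at φ = 0.8 (0.94 − 0.80).

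A reader might go further and infer that the DHI domain scores are contaminated. The documents contain no results that could show this. The change should be made, with medium confidence in its practical effect.

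**What to change.** After the within-domain EFA, tabulate each item's correlation with its own scale (item removed) beside its correlation with every DHI scale in the other domains. Review any item that correlates at least as highly with a scale in another domain, and move or drop it before the all-item CFA. State whether CFA cross-loadings are fixed at zero, and report the factor correlations and the cross-domain modification indices. The factor correlations are needed as well as the table, because a short misfiled group correlates well with itself and is flagged less surely.

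This uses the existing 542 responses. It does not need a pooled EFA of 113 items, which would have 542/113 = 4.8 respondents per item, just under the SAP's own lower figure of 5. The cost is one extra table and a few lines of SAP text. The downside is that a few items may be reassigned or dropped, and the affected scales rescored.

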The primary aim of this research project will be to develop a survey instrument valid to measure health of individuals with Down syndrome ages 0-21 years. As such, the focus is on the psychometric properties of the survey instrument; the study outcomes are the psychometric assessments of the instrument.

Pre-determined Sample Size Calculation and Recruitment Goal

Sample size was determined *a priori* based on the sample size needed to conduct the psychometric analysis. The basic rule of thumb is that (5-10) ten subjects per item are needed for analyses.³⁹ For instance, if the final instrument contains 50 items, 500 subjects are sufficient for 80% power to detect a difference of $\geq .25$ standard deviations using type I error of 0.10. For our DHI with 113 core items, a sample size of 565-1130 caregivers is needed based on using an alpha of .05, a targeted power of .80, and an assumed change of 20% in the score between baseline and follow-up.

Determining “Complete” Surveys

We will closely follow progression through the components of our survey from screening to consent to survey. We considered a survey “Complete” if a participant had a timestamp for completing the DHI section. This occurred when individuals advanced from the final item in the DHI section. Although 683 individuals started the DHI section of our survey, 542 were completed and included in our study.

Item-level Evaluation

Item Distributions (including Missing data)

Ensure no “out of range values” including confirming branching logic followed flow to subsequent questions or skipped as we anticipated / planned.

Basic descriptive statistics are used to report distributions of continuous variables with mean, standard deviation, IQR and frequency for categorical variables. Item distributions evaluated missingness as well as floor and ceiling effects, defined at greater than 85% of responses located in item response anchor. For those with $\geq 85\%$ response at the tails, our research team reviewed the corresponding item and discussed if item should be eliminated. For example, we did not eliminate items related to developmental skills / milestones based on floor and ceiling effects as more than half of individuals are expected to attain some of these skills across the age span studied.

Handling of missing data

Item missingness was evaluated.

Survey-level Evaluation

Scale scoring for all scales/measures:

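### The step the SAP calls a confirmatory factor analysis is, as described, a refit of a model derived from the same single sample, with no stated way to fail; the loadings it reports carry a small upward bias, mainly for items near 0.40.

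*SAP*

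**What the plan says.** In the final SAP, Analysis of Key Psychometric Properties, item 2 (Internal Validity), the order of work is:

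- "Initially, exploratory FA of item grouping within the 3 hypothesized domains (physical, mental, and social health) was conducted to identify factors within each domain",
- then "followed by a confirmatory FA of all items within those factors of all domains".

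The section adds: "The final factor loadings are a result of the confirmatory analysis". On item selection it says: "Items with factor loadings < 0.40 were dropped for low convergent validity". Item 1 (Factor Structure) describes the use of eigenvalues above 1 and loadings above 0.40 as iterative. The SAP does not say whether the 0.40 rule acted after the exploratory step, after the confirmatory step, or at both.

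The only analysis sample described is in the section on determining complete surveys: "Although 683 individuals started the DHI section of our survey, 542 were completed and included in our study". The retest surveys come from people who had already answered, so they are not a second sample.

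The Original Proposed Statistical Analysis Plan (Internal Dimensional validity) had the opposite order. A confirmatory analysis of the hypothesized dimensions came first, and exploratory methods were to be used only if it did not reproduce them.

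**The concern.** A confirmatory factor analysis earns its name by testing a structure fixed before the data were seen, or at least fixed on other data, against a criterion it can fail. Here the factors are found, the items are pruned, and the model is fitted again, apparently on the same surveys. No model-fit index or threshold is given.

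Two things are at stake. First, the SAP states that the study outcomes are the psychometric assessments of the instrument, so the factor structure is itself an outcome. A reader who sees the word confirmatory will credit it with support it does not have. Second, an item kept because its sample loading exceeded 0.40 has, on average, been helped by chance. Re-estimating the loading in the same data keeps that help, so borderline items look better than they are.

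**Working it through.** **1. The plan's own sample-size figure.** The SAP says "The basic rule of thumb is that (5-10) ten subjects per item are needed for analyses" and "For our DHI with 113 core items, a sample size of 565-1130 caregivers is needed".

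- 5 × 113 = 565 and 10 × 113 = 1130, so the range is reproduced by the rule of thumb alone.
- Achieved: 542 / 113 = 4.8 surveys per item, which is 565 − 542 = 23 short of the minimum.
- A half split leaves 271 / 113 = 2.4 per item. A 60/40 split leaves about 325 for derivation (325 / 113 = 2.9) and 217 for confirmation. Keeping 5 per item in both halves would need 2 × 565 = 1130 surveys.

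**2. The two plans side by side.**

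- Original: confirmatory analysis of the hypothesized dimensions first, exploratory only on failure. Its listed criteria (eigenvalues, loadings, scree plots, KMO) include no fit index for the confirmatory model.
- Final: exploratory first, confirmatory second, no fit index.
- Changes to Statistical Analysis Plan: rows for power, complete surveys, item-level evaluation, rotation, test-retest and external validity. None records the reversal, and no result is reported for the hypothesized three-domain model.

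**3. What the exploratory step did not use.** With 113 items there are 113 × 112 / 2 = 6328 inter-item correlations. If the domains are about equal in size (38/38/37, assumed), the cross-domain ones number 38 × 38 + 2 × (38 × 37) = 4256, or 67%. The within-domain exploration used none of these.

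**4. Size of the bias.** The documents give no loadings, so these are assumed. Simulation: one domain of 38 items (113 / 3), n = 542, factor correlation 0.3, eigenvalue > 1, varimax, the 0.40 rule, 60 replicates. One-factor loadings of retained items were then estimated in the same sample and in a fresh sample of 542. Bias = mean in the same sample − mean in the fresh sample. Paired values are principal components, then principal axis; differences were taken before rounding in the first three rows.

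| True loadings | Factors | Same sample | Fresh sample | Bias |
|---|---|---|---|---|
| 0.3–0.8 | 4 | 0.608; 0.614 | 0.604; 0.609 | 0.004; 0.004 |
| 0.2–0.6 | 4 | 0.511; 0.516 | 0.497; 0.504 | 0.014; 0.012 |
| 0.1–0.5 | 6 | 0.466; 0.497 | 0.436; 0.459 | 0.030; 0.038 |
| all 0.40 | 3 | 0.455 | 0.401 | 0.054 |
| all 0.45 | 4 | 0.473 | 0.451 | 0.022 |
| all 0.50 | 3 | 0.502 | 0.498 | 0.004 |

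The 0.1–0.5 row is imprecise: on average only 2.7 and 0.9 of 38 items were retained.

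**5. Retained items below 0.40 in a fresh sample, against a baseline with no selection.** The baseline is a one-factor principal-axis model, n = 542, 300 replicates.

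| True loading | Same sample | Fresh sample | No selection |
|---|---|---|---|
| all 0.40 | 6–8% | 53–54% | 50% |
| all 0.45 | 1–2% | 14–16% | 12% |

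The SD of an unselected loading at true 0.40 was 0.045. A normal approximation with that SD gives Φ(0) = 50% and Φ((0.40 − 0.45) / 0.045) = Φ(−1.11) = 13%, in line with the baseline.

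**The case against.** Four points can fairly be made on the other side.

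*That both steps used the same 542 surveys is nowhere stated.* True. It is inferred from one described sample and the absence of any split. The inference is strong, but the first request should be for the fact itself.

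*The second step is not empty.* A reader might infer that the analysis confirms nothing. That goes too far. The exploration ran inside domains, while the final model covers all of them, so its cross-domain restrictions were not tuned to the data and could in principle be rejected. What remains of the concern is that the SAP gives no model-fit criterion by which rejection would be recognised.

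*The procedure does not invent scales.* In simulated pure-noise items, eigenvalue > 1 kept about 18 of 38 components, but no scale of three or more items survived the 0.40 refit.

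*The damage is small.* A reader who compares 6–8% with 53–54% might conclude that the refit hides the failure of about half the retained items. It does not. Items whose true loading is exactly 0.40 fall below 0.40 about half the time in any fresh sample, selected or not, and they are not misclassified. The excess over the no-selection baseline is only about 2 to 4 percentage points. What stands is the shift in the reported loadings, and the fact that same-sample loadings cannot serve as evidence that borderline items pass.

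**Conclusion.** On the documents, the analysis lacks the confirmatory property the SAP gives it: no independent data and no fit criterion are described. The unlogged reversal of order adds to this, because the hypothesized structure is no longer tested first and its result is not reported.

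The reported loadings of retained items are biased upward, but modestly. The mean bias is about 0.004 to 0.015 if true loadings vary over 0.3–0.8 or 0.2–0.6, about 0.03 to 0.04 if they run from 0.1 to 0.5 (few items retained, so uncertain), and about 0.05 if all sit at 0.40. It matters mainly for items near the cut and is negligible at 0.50.

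These sizes rest on assumed loadings, continuous normal items, varimax rotation only, and one-factor refits in place of a full confirmatory model. The conclusion about the label does not depend on them. Cronbach's alpha, the retest ICCs and the correlations with external measures are separate evidence and do not rest on the word confirmatory.

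**What to change.** 1. State which surveys entered the exploratory step and which the confirmatory step, and at which step the 0.40 rule was applied.
2. Unless independent data were used, stop calling the second step confirmatory and describe it as a refit of the derived model.
3. Bootstrap or repeatedly cross-validate the whole process on the 542 surveys (choice of factors, item dropping, refit). Report optimism-corrected or hold-out loadings for the retained items.
4. Report fit indices for the final all-domain model and for the hypothesized three-domain model, against conventional cut-offs (for example CFI ≥ 0.90, RMSEA ≤ 0.08, SRMR ≤ 0.08). Say openly that these were adopted after the data were analysed.
5. Add the reversal of order to the table of changes.

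The cost is extra analysis of existing data and slightly lower reported loadings; no recruitment is needed. A single 60/40 split is not recommended: 542 is already below the plan's minimum of 565, and derivation on about 325 surveys would make factor recovery and sorting at 0.40 noisier. Repeated cross-validation also derives on reduced samples in each repeat; the bootstrap keeps the full sample size. Neither replaces confirmation in a future independent sample.

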Cover Letter

Official title: Developing a Down Syndrome Health Instrument

NCT Number: NCT04631237

Document Date: 12/16/2024

Developing a Down Syndrome Health Instrument (DHI)

Original Proposed Statistical Analysis Plan:

Power calculation: Sample sizes are based on several criteria. The basic rule of thumb for psychometric analysis (primarily correlation analyses) is 10 subjects per survey item.⁴⁷ The current conceptual model includes 95 items, with refining in SA1, I plan a final item pool of 70 items. The current target sample sizes will support up to 70 variables (items) available for inclusion in psychometric analyses. For instance, if the final instrument contains 70 items, 700 subjects are sufficient for 80% power to detect a difference of $\geq .25$ standard deviations using type I error of 0.10.

Statistical Analyses: A critical aspect of instrument validation, evaluations include:

Distribution evaluation

Ceiling and floor effects: Item response will be evaluated for ceiling and floor effects. Items that exhibit greater than 85% response in the tail of the distribution within severe respondents will be removed. Comparison will be both between and within sample frames.

Internal Validity

- Reliability: This will include comparison between and within sample frames; retest 2-4 weeks later.
- Internal Consistency: Items that are expected to measure a domain or construct should be related to each other in a systematic way. Internal consistency of item groupings will be evaluated with Cronbach's alpha⁵⁸. Values >0.9 will be interpreted to mean an item is simply being asked over and over again and values <0.4 will be viewed as an unacceptable cut-point relative to item differentiation.
- Test-retest Reliability. To test differences among sample means, Tukey's HSD test with threshold alpha ≤ 0.05 will be used to evaluate all items.⁵⁹

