- Internal Dimensional validity: The goal is to identify dimensions of DS health, indicated by factors. Factor analytic methods will be used to identify a factor structure of the DHI. While we may hypothesize what the dimensions of DS health are, a priori this cannot be known. Therefore, we will initially run a confirmatory factor analysis (FA) using our hypothesized dimensions. If the initial CFA does not reveal emergent factors corresponding to the hypothesized factor structure, we will employ exploratory factor analysis (EFA) and principal components analysis (PCA) within hypothesized dimensions or emergent factors. Several criteria will be applied in evaluation of dimensions and factor retention: the Kaiser-Guttman rule (Eigenvalues >1.0), factor loading thresholds of 0.60/.40, scree plots, Kaiser-Meyer-Olkin (KMO) residuals off-diagonal partial correlations measure of sampling adequacy >0.70 .^{52,60,61}

External Criterion Validity: In this proposal, we are seeking to establish validity to draw a valid inference about a distribution and establish some basic inferential validity. External validity will be operationalized using a multitrait-multimethod matrix (MTMM) approach, with the "gold standard" being establishment of forms of both convergent and divergent (discriminatory) validity.⁶² For validation of the DHI, each domain is considered a trait. Method refers to a measurement procedure, which includes consideration of both data source as well as data collection method. The referent method is a caregiver-administered survey. The data source is DHI respondent proxy-report for an individual with DS. The data collection methods include survey instruments and medical record review of clinically-significant metrics, and will be

collected as outlined above in "Population:" (Table 1). Generally, correlation coefficients between DHI domains and data external to the DHI will be used as evaluative criteria, with the specific correlation statistic being determined by the test value variable type. Utilization of the MTMM allows evaluation of correlation within and between methods and sources as well as within and between dimensions or traits.

Final Statistical Analysis Plan:

Planned Method of Analysis

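### The Final SAP screens for redundant items only by a factor loading above 0.9, which can miss near-duplicate item pairs, depending on scale length and estimator

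*SAP*

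**What the plan says.** The Final SAP, under Analysis of Key Psychometric Properties, uses factor loadings to decide which items stay.

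- **Retention (Factor Structure).** "We used standard criteria (eigenvalues > 1) and items within factors (factor loading scores > 0.40". Principal components and principal factor analysis are the named extraction methods.
- **Weak items (Internal Validity).** "Items with factor loadings < 0.40 were dropped for low convergent validity".
- **Redundant items (Internal Validity).** "items with loadings > 0.9 were reviewed for redundancy and dropped as appropriate".
- **Which loadings count.** "The final factor loadings are a result of the confirmatory analysis". The estimator for that confirmatory analysis is not stated.
- **Internal consistency.** "Internal consistency was evaluated with Cronbach's alpha". No acceptance limit is given.

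The Original Proposed SAP, printed in the same file, is superseded. It placed its redundancy limit on alpha: "Values >0.9 will be interpreted to mean an item is simply being asked over and over again". For the low end it said that "values <0.4 will be viewed as an unacceptable cut-point relative to item differentiation". It also listed "factor loading thresholds of 0.60/.40" for the factor analysis. The table of changes at the end of the SAP does not mention that the redundancy rule moved from alpha to loadings.

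**The concern.** The Final SAP states that the study outcomes are the psychometric assessments of the instrument. The rules that keep or delete items therefore play the part that an endpoint definition plays elsewhere.

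A redundancy rule should find two questions that ask the same thing. A high loading does not show this. An item can load above 0.9 with no duplicate, and two near-identical items can each load well below 0.9 when the factor is defined mainly by other items.

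A duplicate that stays counts one symptom twice, because DHI scores are built from item means. In an 8-item scale a duplicated symptom carries 2/8 = 25% of the weight, against 1/7 = 14% if one of the two items is removed.

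There is a second risk. If the fitted factor collapses onto the duplicate pair, the remaining sound items can fall below 0.40 and be dropped as weak.

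**Working it through.** The cut-offs are decision rules, so the plan has no figure of its own to reproduce. The check asks what the rules do on constructed scales.

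**Inputs from the Final SAP.** Loading above 0.9 triggers redundancy review; loading below 0.40 drops the item; eigenvalue above 1 retains the factor.

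**Assumed, because the documents do not give them.** Scales of 2 to 15 items, true loadings L of 0.40 to 0.75, and one duplicate pair with correlation r = 0.95.

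**Step 1. Pure one-factor model.** Two items with loadings L1 and L2 correlate L1 × L2. At the limit, 0.90 × 0.90 = 0.81. Without any extra overlap between the items, pairs correlated up to 0.81 are not flagged.

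**Step 2. A near-duplicate pair inside a longer scale.** Each correlation is set to L², and one pair is raised to 0.95. One factor is then fitted. "items with loadings > 0.9 were reviewed for redundancy and dropped as appropriate" applies only if the pair's loading exceeds 0.9.

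| Items | True L | Pair loading, principal factor (iterated / one-step) | Pair loading, ML | Other items' loading, ML |
|---|---|---|---|---|
| 4 | 0.60 | 0.96 / 0.95 | 0.98 | 0.37 |
| 8 | 0.60 | 0.78 / 0.86 | 0.97 | 0.38 |
| 8 | 0.75 | 0.83 / 0.87 | 0.97 | 0.61 |
| 10 | 0.75 | 0.81 / 0.85 | 0.85 | 0.73 |
| 15 | 0.60 | 0.68 / 0.74 | 0.70 | 0.59 |
| 15 | 0.70 | 0.75 / 0.79 | 0.76 | 0.69 |
| 15 | 0.75 | 0.79 / 0.82 | 0.80 | 0.75 |

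The same pair is flagged by both methods at 4 items. At 8 items it is flagged by ML only. In the 10-item case at 0.75 and in all the 15-item cases neither method flags it.

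**Step 3. Side effect when ML flags the pair.** In the 8-item scale at 0.60, the six sound items have fitted loadings of 0.38. Applied literally, the 0.40 rule would drop all six. With true loadings of 0.75 they stay at 0.61, so this happens only when the other items are moderate.

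**Step 4. Would a pairwise check find it?** The inter-item correlation is 0.95 in every row, so any limit near 0.80 finds it. The residual correlation is r minus the squared pair loading:

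- 8 items at 0.60, iterated principal factor: 0.95 − 0.78² = 0.34, clearly visible.
- 15 items at 0.60, ML: 0.95 − 0.70² = 0.46, clearly visible.
- 8 items at 0.60, ML: 0.95 − 0.974² ≈ 0.00, invisible, because the factor has become the pair.

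The residual check alone is therefore not enough; the plain inter-item correlation is also needed.

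**Step 5. Secondary point, alpha at the lower limit.** With k items all loading 0.40, the mean inter-item correlation is 0.16 and alpha = k × 0.16 / (1 + (k − 1) × 0.16).

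- k = 2: 0.32/1.16 = 0.28
- k = 3: 0.48/1.32 = 0.36
- k = 4: 0.64/1.48 = 0.43

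So 2- or 3-item scales can satisfy the loading rule with low alpha. The eigenvalue rule may stop them. On the reduced matrix the eigenvalues are 2 × 0.16 = 0.32 and 3 × 0.16 = 0.48, which fail. On the unreduced matrix they are 1.16 and 1.32, which pass. The SAP does not say which matrix is meant.

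**The case against.** **The rule often works.** Under ML the pair reaches about 0.97 in both 8-item examples and is sent to review. In the 4-item example it is flagged by either method. The loadings that count are the confirmatory ones, so principal-factor results are not decisive. The rule also triggers a team review, and a team developing scales iteratively could spot two near-identical questions by reading them. This stands, and it limits the point to saying that the rule can miss duplicates. It does not rescue the rule, because the estimator is unstated and longer scales defeat ML as well.

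**The 0.4 and 0.9 limits might look like a contradiction, on alpha in one place and on loadings in another.** The documents do not support that reading. The alpha limits belong to the superseded plan and only the Final SAP is in force. The 0.40 loading threshold already stood in the Original plan ("factor loading thresholds of 0.60/.40"), so only the 0.9 limit on loadings is new.

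**A reader might infer that a working screen was lost.** It was not. In the 8-item scale at 0.60 with the duplicate, alpha is 0.83, so a limit of 0.9 misses it. At 0.75 alpha is already 0.91 with no duplicate, so the limit flags a sound scale. Nor does the duplicate inflate alpha much: from 0.818 to 0.831 in the first case and from 0.911 to 0.916 in the second.

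**A reader might also infer that scales with alpha below 0.4 are kept.** On a one-factor model this needs 2 items loading about 0.40 to 0.50, or 3 items at about 0.40 to 0.43, and the eigenvalue rule may exclude even those.

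**Conclusion.** The concern holds in a limited form. The Final SAP's only stated redundancy screen measures an item's link to its factor, so it can miss near-duplicate pairs. Whether it does depends on scale length, on the strength of the other items and on an estimator that the plan does not name. For a pair correlated 0.95, the loading ranges from 0.68 (missed) to 0.98 (flagged) across the cases examined. Where ML flags the pair among moderate items, the 0.40 rule may remove sound items instead.

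This rests on one-factor illustrations with equal loadings and a single duplicate pair. The actual confirmatory model covers all domains at once. Scale lengths, loadings and inter-item correlations are not in the documents, so no DHI scale is shown to contain a missed duplicate or to have lost items wrongly. The absent alpha minimum and the unlisted change of rule are secondary matters of detail and record-keeping.

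**What to change.** In the Final SAP, Internal Validity:

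1. **Screen redundancy on item pairs.** Review pairs with a high inter-item correlation (for example above 0.80) or a large positive residual correlation in the confirmatory analysis. Use this in place of, or in addition to, the loading limit of 0.9. The 0.80 is a suggested working value, not a figure from the documents.
2. **Set the order.** Resolve flagged pairs first, refit, and only then apply the 0.40 drop rule.
3. **Name the confirmatory estimator.**
4. **Secondary.** Report alpha with a 95% confidence interval for each scale against a stated minimum. Add the change of redundancy rule, with its reason, to the table of changes.

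The cost is one correlation table from the 542 completed surveys already held, a refit where a pair is resolved, and a few more items for the team to review. No new data are needed. Some short scales may have to be reported as falling short of the stated alpha minimum.
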